Effects of the probiotic k11-tmax on symptoms and inflammatory markers in children with autism spectrum disorder

GON1
PESQUISA & BIOTECNOLOGIA

[figure not shown]
March, 22th of 2024.

EFFECTS OF THE PROBIOTIC K11-TMAX ON SYMPTOMS AND INFLAMMATORY MARKERS IN CHILDREN WITH AUTISM SPECTRUM DISORDER

SUMMARY

Disorder Autism is a neurological disorder that affects social, communication, and behavioral development. Since the initial description of the disorder by Kanner (1943), there has been a wide range of research on autism, including genetic, neurobiological, behavioral, and intervention studies. The exact cause of autism is not fully understood, but studies indicate that genetic and environmental factors may be involved, while some studies suggest that metabolic indices of serotonin, dopamine, amino acids, among others, may be affected, while others suggest that genetic predisposition is an important factor in the origin of autism. Ding et al. (2021) discuss evidence of imbalances in intestinal microbiota with autism development. Conducting a literature review, various pieces of evidence suggest that inflammatory processes may contribute to the development and symptoms of autism. In this context, metabolic deficiencies, inflammatory processes, and intestinal dysbiosis may be directly related to autism and its symptoms. The connection between gut microbiota and the nervous system occurs through the gut-brain axis, a well-established association in the scientific community. Numerous studies have investigated the effects of probiotics on intestinal and mental health, including the production of neurotransmitters such as dopamine and serotonin. This has been documented in research conducted by Marco et al. (2015), Xie et al. (2020), Dinan et al. (2013), among others. These findings underscore the importance of understanding the role of probiotics in modulating gastrointestinal health and mental well-being. Similarly, Martins et al. (2022) concluded that there is a significant association between inflammatory bowel disease and autism. We propose a clinical trial to evaluate the effects of a probiotic called nanoencapsulated K11-Tmax on improving symptoms and inflammatory biomarkers in children with ASD.

Keywords: Autism; Biomarkers; Inflammation; Probiotics; Gut Microbiota

1. THEORETICAL FRAMEWORK

The autism spectrum disorder (ASD) is a complex and multifaceted condition, with many different definitions provided by scientists and researchers. According to Kanner (1943), autism is a separate and distinct condition from other psychiatric conditions. Kanner described autism as a condition characterized by "an inability to establish emotional contact with other people, a lack of desire to establish social relationships, an inability to use language to communicate experiences, and ritualistic and stereotyped behavior." These characteristics are still widely recognized as part of the definition of autism, although the understanding of the condition has evolved significantly since Kanner's time.¹⁵

Another important definition of autism was provided by Hans Asperger (1944),²² an Austrian pediatrician who first described what is now known as Asperger's syndrome. In 1944, Asperger published a paper titled "Autistic Psychopathy in Childhood," in which he described a group of children who shared characteristics like those described by Kanner. However, Asperger emphasized the importance of recognizing the exceptional abilities and talents of these children, rather than just focusing on their difficulties. He described the children as having "special intelligence," with skills in areas such as memory, visual perception, and mathematics. He also noted that these children often had intense and restricted interests, which could become a source of creativity and achievement.²²

Asperger's definition became significant as Asperger's syndrome was recognized as a subtype of autism. Although Asperger's syndrome is no longer a separate diagnostic category in the DSM-5 (Diagnostic and Statistical Manual of Mental Disorders, 5th edition), many people still use the term to refer to a specific type of autism that includes exceptional skills and talents in some areas.²³ Various studies have been conducted to better understand autism, from its etiology to clinical intervention. One prominent area of research is neuroscience, which seeks to understand the neurological changes that may be associated with autism. Brain imaging studies, for instance, have demonstrated differences in connectivity and brain activity, as well as in neuroendocrine and metabolic aspects, in individuals with autism compared to typical individuals.^{2,3,5,8,10,24}

Although there is no formal classification of "autism levels," many autism specialists use terms like "high-functioning" or "low-functioning" to describe different degrees of autism's impact on a person's daily life.^{11,15,7,18,22,25} Tony Attwood (1998) discusses the different levels of functioning within the autistic spectrum, stating that autism is a continuous spectrum, with some people experiencing severe difficulties in areas such as communication and social skills, while others have fewer difficulties in these areas but may still exhibit repetitive and restricted interests and behaviors. He also emphasizes the importance of understanding that each person with autism is unique and may present a wide variety of symptoms and needs.²⁴

Kanner (1943)¹⁵ was the author who defined the symptoms of autism as being divided into three main areas:

- Communication: difficulty initiating and maintaining conversations, stereotyped use of language, difficulty understanding context, and interpreting nonverbal language.
- Social interaction: difficulty in developing and maintaining relationships, lack of interest in shared play, lack of empathy, and understanding of others' emotions.
- Restricted and repetitive behaviors: repetitive or ritualized behaviors, intense interest in specific topics, difficulty coping with changes in routine, hypersensitivity to sensory stimuli (such as light, sound, and textures).

It is important to note that not all people with autism exhibit the same symptoms and that they can vary widely in intensity and frequency. Some individuals with autism may have milder

symptoms and be able to live independently, while others may require constant support in their daily activities.^{15,18,24,25}

Several hypotheses have been proposed to explain inflammation related to ASD.¹ The dysregulation of the maternal immune system during pregnancy has been implicated, and the transfer of maternal fetal brain-reactive antibodies is associated with an increased risk of ASD.² In maternal autoimmunity, IgG antibodies derived from the mother enter the fetal compartment freely crossing the placenta; these antibodies recognize proteins and can interfere with fetal development.^{4,7}

The gastrointestinal system has a direct connection with the immune system. Gastrointestinal symptoms associated with ASD may be a manifestation of an underlying inflammatory process.^{3,12,26,27} Increased intestinal permeability has been associated with ASD (leaky gut hypothesis).^{4,28,29} A landmark study detected increased intestinal permeability in 37% of autistic patients and in 21% of their relatives through the lactulose/mannitol test. Interestingly, autistic individuals on a gluten-casein-free diet had significantly lower intestinal permeability than those on an unrestricted diet and control individuals. Calprotectin was used as a non-invasive marker to assess intestinal inflammation.^{5,30,31,32,33} Intestinal barrier defects predispose individuals with ASD to sensitization by environmental antigens. Notably, the abnormal immune system in autistic individuals may be due to gluten/casein-derived molecules that, once moved to a damaged intestinal barrier, trigger pro-inflammatory processes (increased pro-inflammatory cytokines and pro-inflammatory monocytes).^{6,13,34,35} These pro-inflammatory mediators or immune-activated complexes reach higher brain centers through the bloodstream, and a permissive blood-brain barrier further contributes to neuroinflammation events.^{7,37,38,39}

Growing evidence supports dysbiosis of the intestinal microbiota in ASD. Through cultivation methods, aggressive forms of *Candida* spp. were identified in the stools of 57% of children with ASD and not in healthy controls of the same age.⁹ Decreases in *Lactobacillus* spp. and *Clostridium* spp. could sustain dysbiosis. Different fecal flora was observed in regressive autism compared to normal controls.¹⁰ Harmful intestinal colonizing microorganisms produce various chemicals from their cell cycles that affect behaviors, as these metabolites have molecular structures similar to brain neurotransmitters.^{11,40,41,42} In summary, inflammatory state, cellular viability, and genetic factors are intrinsically related to ASD, and the increasing understanding of these mechanisms underscores the need to explore new directions for future treatments and therapies for ASD.

2. GENERAL OBJECTIVE

The objective of this study is to evaluate the effectiveness of probiotic compounds K11-T and K11-Tmax (enriched with amino acids, minerals and vitamins), in their solid and nanoencapsulated formulations, in improving neuropsychological, psychiatric and psychopedagogical outcomes, as well as reducing inflammatory parameters in children with ASD.

3. SPECIFIC OBJECTIVES

- Characterize the sample of individuals with ASD who will participate in the study through a questionnaire with sociodemographic and pedagogical data such as: Age in years; gender in percentage terms of the sample according to female or male; Weight in kg; Height in centimeters; Time since diagnosis of ASD in years and presence of psychiatric or neurological comorbidities in percentage terms of the sample.

- Investigate the association between probiotic consumption and neuropsychological results using the scale unit validated in the literature Vineland Adaptive Behavior Scales - Third Edition (Vineland-3) in the questionnaire format answered by parents/guardians of the child with ASD;
- Investigate the association between probiotic consumption and the change of psychiatric parameters through the application of the validated Autism Diagnostic Observation Schedule (ADOS) scale with children with ASD;
- Investigate the association between probiotic consumption and the change of psychopedagogical parameters using the Childhood Autism Rating Scale (CARS) validated in the literature, which will be answered by the teachers responsible for each child participating in the study;
- Analyze the possible effect of probiotics on inflammatory aspects in individuals with ASD, through serum (Insulin, C-Reactive Protein, Prolactin and Cortisol) and fecal (fecal calprotectin) biomarkers;
- Analyze the difference of using the K11-Tmax version, enriched with supplements, on the neuropsychological, psychiatric and psychopedagogical outcomes described above in comparison to the group that used K11-Tmax alone with the presence of a control group that will receive placebo.

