4.2. EXPERIMENTAL PROTOCOL

4.2.1. Study Design

This study will be conducted in a medical clinical specifically adapted for testing and with a permissive playful space to mitigate the stress of the involved children and avoid social conflicts during evaluation sessions. The space will comprise at least 17 individual analysis rooms, and the evaluation will involve 20 neuropsychologists, 2 pediatricians and 1 psychiatrist with prior and ensured training.

Children will be evaluated on DAY 0, DAY 45 and DAY 90 to quantify inflammatory markers through blood collection; for measuring fecal calprotectin, by collecting fecal samples; and finally, for the primary outcomes mentioned in this project: neuropsychological (Vineland-3); psychiatric (ADOS) and psychopedagogical (CARS). After the first data collection, individuals will be randomized to receive the K11-T probiotic mixture or the K11-Tmax probiotic mixture or placebo, in a 1:1:1 ratio. After the initial 90-day follow-up, up to 30% of the sample using K11-Tmax will continue to be monitored, being re-evaluated after 365 days in all aspects mentioned. Children will be stratified by age, gender and level of support (see Appendix B) and then randomized to intervention according to the groups below.

Condition or Disease	Intervention/Treatment	Phase
Children with ASD	Drug 1: Probiotic K11-T Drug 2: Probiotic K11-Tmax Drug 3: Placebo	Phase 3

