4.2.3. Quantification of C-reactive Protein (CRP)

For the quantification of PCR, individuals were instructed to fast for 8 hours. Polymerase Chain Reaction (PCR) is a widely used technique for amplifying specific DNA sequences in vitro. It allows selective and rapid amplification of a target DNA region, enabling its detection and analysis. The PCR methodology involves the following steps:

- Reaction preparation: Reaction components are prepared in a reaction tube, including the target DNA, primers (specific oligonucleotides that bind to sequences of interest), nucleotides (DNA building blocks), a DNA polymerase enzyme (which catalyzes DNA synthesis), and a reaction buffer providing optimal conditions for enzyme activity.
- Denaturation: The reaction mixture is heated to a high temperature (usually between 94-98°C) to denature the target DNA, separating the two complementary strands.
- Primer Annealing: The temperature is reduced (usually between 50-65°C) to allow the primers to anneal (bind) to the complementary DNA sequences at the ends of the target.
- Extension: The temperature is then raised again (usually around 72°C) to enable the activity of the DNA polymerase enzyme. The enzyme synthesizes a new complementary DNA strand to each of the original strands.
- Amplification cycles: The denaturation, annealing, and extension steps are repeated in successive cycles. Each cycle doubles the number of copies of the target DNA. The total number of cycles may vary depending on the desired amount of amplification.
- At the end of PCR, multiple copies of the target DNA sequence are obtained, allowing for its subsequent detection and analysis. Amplification can be visualized using various methods such as agarose gel or capillary electrophoresis, and detection can be performed using fluorescent probes, specific dyes, or DNA sequencing.

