4.2.7. Fecal Calprotectin Measurement

The sample for fecal calprotectin measurement will be collected by convenience sampling, considering the inherent behavioral difficulties of the disorder, while respecting a minimum sample value of 30% of the total sample of children, totaling at least 81 children. Families will be instructed to collect the first stool of the day and keep it refrigerated at a temperature ranging from 4 to 5 degrees Celsius (in a regular refrigerator) until the evaluation time. Children undergoing colonoscopy, using laxatives or suppositories, or undergoing examinations using radiological contrasts within 72 hours before collection will have their samples discarded. The fecal material will be stored in a refrigerated environment, processed using a specific kit for measurement, and expressed in µg/g.

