4.2.11. Biostatistics

Mean and SD (standard deviation) will be used to describe quantitative data, while risk factors, frequency and percentage will be used to describe qualitative data. Shapiro-Wilk test will confirm or not the normality of data distribution in the groups, therefore, parametric, or non-parametric tests, respectively, will be used to assess the research variables. To compare quantitative variables in the two or more groups, independent t-test (between groups) or paired samples t-test (within groups), ANOVA (between groups) or Repeated Measures (within groups), with post hoc testing to assess individual differences among the categories, will be used as parametric options. The relatives nonparametric options will be used otherwise and chi square test, if qualitative variables. All statistical calculations will be performed at the significance level of less than 0.05 (P < 0.05). Data will be analyzed using SPSS version 26.0.

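### Insulin, prolactin and cortisol are classed as inflammatory biomarkers without argument, so a hormone change alone could be reported as an effect on inflammation

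*Protocol*

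**What the plan says.** Section 2 (General Objective) includes, among the study's aims, "as well as reducing inflammatory parameters in children with ASD". It names no marker.

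Section 3 (Specific Objectives) names them. The probiotics' possible effect is to be analysed on "inflammatory aspects in individuals with ASD, through serum (Insulin, C-Reactive Protein, Prolactin and Cortisol) and fecal (fecal calprotectin) biomarkers". The five markers are listed side by side, with none ranked above another. The wording here states no direction.

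Section 4.2.1 (Study Design) says that children are assessed on days 0, 45 and 90 "to quantify inflammatory markers through blood collection; for measuring fecal calprotectin, by collecting fecal samples". The inflammatory label is thus given to the blood tests as a group, with calprotectin listed after them. The same section names Vineland-3, ADOS and CARS as the primary outcomes.

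Sections 4.2.4 to 4.2.6 describe cortisol, insulin and prolactin as chemiluminescence assays, each with its own unit, and say nothing about what they represent. Section 1 (Theoretical Framework) says of the fecal marker: "Calprotectin was used as a non-invasive marker to assess intestinal inflammation".

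**The concern.** An objective is only as good as the measurements that stand for it. Most of the markers chosen here for inflammation are hormones. If insulin, prolactin or cortisol differed between arms while CRP and calprotectin did not, the protocol's own classification would let that be written up as a finding on inflammation. It would then appear to support the gut-inflammation rationale on which the trial is built.

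The hormone difference could be entirely real and the inference still wrong. This is a question of what is measured, so neither a larger sample nor a stricter significance level would cure it. What is at stake is a mechanistic conclusion, not the conclusion on the primary behavioural scales.

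**Working it through.** The protocol states no figure for this point, apart from the calprotectin minimum. The check is therefore a count, a side-by-side reading and one small reproduction.

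**1. Count of markers (section 3).**
- All markers: insulin, CRP, prolactin, cortisol, calprotectin = 5.
- Hormones: insulin, prolactin, cortisol = 3. Share: 3/5 = 60%.
- Serum markers: 4, of which 3 are hormones. Share: 3/4 = 75%.
- Left as markers of inflammation: CRP and calprotectin = 2 of 5.

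The one premise from outside the text is that these hormones do not in themselves measure inflammation.

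**2. Does the protocol argue for the hormones?**
- Section 1 connects inflammation with calprotectin, pro-inflammatory cytokines and pro-inflammatory monocytes. It mentions none of the three hormones.
- Section 1 also refers to neuroendocrine and metabolic differences in autism. That is background for measuring hormones, not a reason to call them inflammatory.
- Sections 4.2.4 to 4.2.6 give assay methods only.
- Section 5 (Justification) speaks of chronic inflammation and immune dysfunction, again without the hormones.

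**3. Does any rule prevent a hormone-only claim?** Section 4.2.11 applies a 0.05 level to all calculations. No section says that CRP or calprotectin must change before the inflammation objective is supported, and no section says that a hormone change would be enough. The protocol leaves this open, so the supportable wording is that such a claim could be made.

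**4. What is left once the claim is narrowed.**
- Calprotectin: section 4.2.7 describes convenience sampling "respecting a minimum sample value of 30% of the total sample of children, totaling at least 81 children". Reproduced: 0.30 × 270 = 81. If spread evenly over three arms, 81/3 = 27 per arm, against 270/3 = 90 per arm for a marker measured in everyone.
- Smallest difference detectable with 80% power at two-sided 0.05, in SD units, is (1.960 + 0.842) × √(2/n). For n = 90: 2.802 × 0.149 = 0.42 SD. For n = 27: 2.802 × 0.272 = 0.76 SD. This assumes one pairwise comparison, an even split and no dropout.
- CRP: section 4.2.3 is headed C-reactive protein, but its text says "Polymerase Chain Reaction (PCR) is a widely used technique for amplifying specific DNA sequences in vitro". It goes on to describe primers, denaturation and amplification cycles. That is not a method for measuring a serum protein.

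**5. A calculation not relied on.** With three independent tests at 0.05 and no true effect, the chance of at least one significant hormone is 1 − 0.95³ = 14.3%. Any three markers, including genuine inflammatory ones, would give the same figure. It describes multiplicity and does not measure the misclassification.

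**The case against.** The strongest case on the other side is that this is a loose heading on secondary measures. The direction of benefit appears in section 2, which names no marker; section 3 names the markers but is neutral on direction. Section 4.2.1 names no hormone. There is no composite and no rule that any one of five suffices. Each hormone has its own section and unit, so a reader of the results could see which marker moved. A rule for interpreting the markers may stand in a statistical analysis plan that is not at hand.

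Most of this stands, and it limits the point. It does not remove it, because the classification itself is made in the protocol's objectives and is not a detail deferred to an analysis plan.

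A reader might infer more than the text supports in four ways:
- **That the protocol counts a fall in every marker as benefit.** It does not. That reading joins sections 2 and 3.
- **That a fall in cortisol would only show children becoming used to the visits.** In comparisons between arms, randomization and placebo should balance habituation. The worry applies only to the within-group tests that section 4.2.11 also plans.
- **That the budget in section 7 shows the sponsor already classes the hormones as non-inflammatory**, because it has separate lines for inflammatory and biochemical tests. The table does not assign any assay to either line.
- **That CRP will not be measured at all.** Section 3 and the heading of section 4.2.3 both name it, so the documents show a contradiction to be reconciled and not a dropped marker.

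**Conclusion.** The point holds as a misclassification stated in the protocol: 3 of the 5 biomarkers assigned to the inflammation objective, and 3 of the 4 serum ones, are hormones for which no link to inflammation is argued. A change in one of them alone could be reported as an effect on inflammation. It would go too far to say that it will be, or that the protocol defines it as success.

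The consequence is confined to the mechanistic claim, and conclusions on the primary scales are untouched. The verdict rests on the premise that a hormone change alone is not evidence of changed inflammation, and on the absence of any contrary rule in the protocol. An unseen analysis plan could restrict the claim, but the objectives would still need rewording.

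**What to change.** - In sections 2, 3 and 4.2.1, limit the inflammation objective, and any claim about inflammation, to CRP and fecal calprotectin. State there that calprotectin comes from a convenience subset with a minimum of 81 of 270 children.
- Move insulin, prolactin and cortisol to a separate exploratory endocrine and metabolic objective with no stated direction of benefit. Add that a change in them will not be reported as a change in inflammation; for cortisol, this covers within-group change over visits too.
- Reconcile the heading and text of section 4.2.3, so that the retained CRP marker is described as a protein assay with its unit. Without this, the narrowed claim would rest on a marker whose method is wrongly described.

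The reclassification costs only wording; all five tests are still done and no data are lost. The price is a narrower inflammation claim, resting on two markers, one of them from a limited and non-random subset.
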